14.1.2.2 Sensitivity Analyses of SRI-4 and SRI-6

The following sensitivity analyses are planned to be performed using different approaches to the missing data handling from the primary analysis.

Sensitivity Analysis #1: Per Protocol Analysis

The primary analysis method including the missing data handling approach for the two-primary endpoints will be repeated on the PP Analysis Set if the size of this analysis set differs substantially (>10%) from mITT.

For this analysis, the estimated OR, together with associated two-sided 95% CI of the estimated OR and nominal p-value from the logistic regression model, comparing each evobrutinib treatment group to placebo will be presented.

In addition, the number and percentage of SRI-4/SRI-6 responders and non-responders at Week 52 in each treatment group will be presented the same way as for the primary analysis (see Section 14.1.2.1).

Sensitivity Analysis #2: MI

In this analysis, a subject will be considered as a non-responder if using EAC-determined protocol prohibited medications (i.e., EAC-treatment failure). For subjects with missing response at Week 52, then the MI will be used to impute the missing data using the available observations from previous visits and from components of SRI-4/SRI-6 response and also stratification factor used in primary analysis.

The MI analysis will include the components as described below:

1. SLEDAI-2K change from baseline total score will be imputed using SAS MI procedure (including 2 other components: PGA score and BILAG response) and then the occurrence of a ≥ 4 -point reduction will be re-derived from the imputed values. For the SRI-6 the occurrence of a ≥ 6 -point reduction will be also re-derived from the imputed values.
2. PGA score will be imputed using SAS MI procedure (including 2 other components: SLEDAI-2K change from baseline and BILAG response), assuming the distribution is approximately normal. The imputed values will be transformed to a 0-3 scale:
 - i. Negative values will be imputed as 0,
 - ii. Values > 3 will be imputed as 3.
 - iii. The imputed score will then be used to calculate whether there was significant worsening in the PGA score.
3. Whether there was no new BILAG A organ domain scores and ≤ 1 new BILAG B organ domain score compared to Day 1 will be considered as a dichotomic response with value 1 when it is met and 0 otherwise. This score will be imputed using SAS MI procedure (including 2 other components: SLEDAI-2K change from baseline and PGA score) and the response will be deducted from the logic below:
 - i. Values < 0.5 will be imputed as 0,
 - ii. Values > 0.5 will be imputed as 1.

Components no. 1 to 3 will be imputed assuming a MAR pattern. The SAS MI procedure will be performed as follows:

- Monotone missing data structure will be created as follows: intermediate (non-monotone) missing data will be multiply imputed using the Markov chain Monte Carlo (MCMC) method and assuming MAR and multivariate normality. The SAS procedure PROC MI with the MCMC option will be used with seed number = 2005270018. The number of burn-in iterations will be set to 200, which is the default value. Nevertheless, if diagnosis plots show that the convergence has not yet occurred, this will be adjusted.
- Then, each component will be imputed with treatment group, race, region, SLEDAI-2K total score (<10 ; ≥ 10) and data at previous visit from all SRI components as covariates.

- Imputation will be repeated 1000 times. The SRI response will then be calculated for each of the multiply imputed data sets from the imputed components. For this analysis, the estimated OR, together with associated two-sided 95% CI of the estimated OR and nominal p-value from the logistic regression model, comparing each evobrutinib treatment group to placebo will be presented. Results will be combined using MIANALYZE SAS procedure with the Rubin's rules as described in Appendix 18.9.

The SAS code to implement the MI and MIANALYZE procedures is in Appendix 18.9.

The same analysis method as the primary analysis of the two-primary endpoints will be performed using the mITT Analysis Set for SRI-4 and in the HDA subject subgroup for SRI-6.

In addition, the number and percentage of SRI-4/SRI-6 responders and non-responders at Week 52 in each treatment group will be presented the same way as for the primary analysis (see Section 14.1.2.10) using Rubin's rules to gather binomial proportion by each treatment (see Appendix 18.9).

Sensitivity Analysis #3: Tipping Point Analysis

For this analysis, a subject will be considered as an SRI-4 or SRI-6 Non-Responder if the subject takes EAC-determined protocol-prohibited medications during the treatment period (i.e. EAC-treatment failure).

Tipping point analysis will be performed as in Yan 2009, Section 2.3.2.

All possible combinations of success/failure may be posited in the 4 treatments groups. Results are obtained by a random single imputation of possible scenarios (responder or non-responder) to each arm. All possible combinations of imputations of response among subjects with missing response in the placebo group and evobrutinib 25 mg QD, 75 mg QD and 50 mg BID groups. For each combination, the imputed data were combined with the data from subjects with non-missing data and primary analysis.

Assumptions of missing data due to a missing response at Week 52 will be varied to see if there are any tipping points:

Let

$n_1 =$ number of responders out of missing data due to various reasons for placebo

$n_2 =$ number of responders out of missing data due to various reasons for evobrutinib 25 mg QD

$n_3 =$ number of responders out of missing data due to various reasons for evobrutinib 75 mg QD

$n_4 =$ number of responders out of missing data due to various reasons for evobrutinib 50 mg BID

The same analysis method as the primary analysis of the two-primary endpoints will be performed using the mITT Analysis Set for each possible combination of n_1 , n_2 , n_3 and n_4 .

The values of n_1 , n_2 , n_3 and n_4 where the study result will be tipped from statistically significant (not statistically significant) to not statistically significant (statistically significant) will be assessed for plausibility based on the corresponding response rate from each treatment. See Section 14.1.2.4 for the multiplicity adjustment procedure.

Sensitivity Analysis #4: Unadjusted Analysis

The analysis of the two-primary endpoints will be performed on the mITT Analysis Set.

In this analysis, the logistic regression model will be used with only treatment as a factor.

For this analysis, the estimated OR, together with associated two-sided 95% CI of the estimated OR and nominal p-value from the logistic regression model, comparing each evobrutinib treatment group to placebo will be presented.

In addition, the number and percentage of SRI-4/SRI-6 responders and non-responders at Week 52 in each treatment group will be presented the same way as for the primary analysis (see Section 14.1.2.1).

Sensitivity Analysis #5: Analysis including the background therapy of immunosuppressant

This sensitivity analysis of the SRI-4 response at Week 52 among all subjects, and SRI-6 response at Week 52 among HDA subjects, will be based on the mITT Analysis set, and analyzed using logistic regression model for the odds of a given SRI response adjusted for the stratification variables used in the randomization (race: black vs non-black, screening SLEDAI-2K total score: <10 vs ≥ 10 and region: US and Western Europe vs Japan vs ROW), background therapy of immunosuppressant (Yes/No) as covariate and with treatment as a factor.

Background therapy of immunosuppressant will be derived at Day 1 using concomitant medications data with class = "Immunosuppressant", Anatomical Therapeutic Chemical (ATC) code level 3 = L04A.

For this analysis, the estimated OR, together with associated two-sided 95% CI of the estimated OR and nominal p-value from the logistic regression model, comparing each evobrutinib treatment group to placebo will be presented.

In addition, the number and percentage of SRI-4/SRI-6 responders and non-responders at Week 52 in each treatment group will be presented the same way as for the primary analysis (see Section 14.1.2.1).

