18.1.3 SLEDAI-2K

The Total score of the SLEDAI-2K is calculated as the sum of the weights of the descriptors marked as present by the investigator. The weights corresponding to each of the 24 descriptors are described in the table below:

Table 33: SLEDAI scoring

Descriptor	Weight
Seizure	8
Psychosis	8
Organic brain syndrome	8
Visual disturbance	8
Cranial nerve disorder	8
Lupus headache	8
Cerebrovascular accident	8
Vasculitis	8
Arthritis	4
Myositis	4
Urinary casts [#]	4
Hematuria [#]	4
Proteinuria [#]	4
Pyuria [#]	4
Rash	2
Alopecia	2
Mucosal ulcers	2
Pleurisy	2
Pericarditis	2
Low complement* [#]	2
Increased DNA binding* [#]	2
Fever	1
Thrombocytopenia [#]	1
Leukopenia [#]	1

*blinded descriptor

[#]laboratory components

Handling with blinded descriptor: As “Increased DNA binding” and “Low complement” are blinded items, the SLEDAI-2K total score will have to be derived for primary analysis with the laboratory unblinded values. “Increased DNA binding” item is defined as “>25% binding by Farr assay or above normal range for testing laboratory”. The parameter to take into account in laboratory data is “anti-Double Stranded DNA”. Increased DNA binding will be derived as ‘present’ if the anti-dsDNA value is positive (i.e. > 15 U/mL). “Low complement” item is defined as “decrease in C3 or C4 below the lower limit of normal for testing laboratory”. The parameters to take into account in laboratory data are “Complement C3” and “Complement C4”.

Total score used for statistical analysis will be re-calculated for all timepoints except screening and Day 1 with the unblinded values of Increased DNA binding and Low complement. The total score for the next visits as stated by the investigator in the eCRF will not be used in any statistical analysis.

Handling of missing items in SLEDAI-2K scores and change from baseline scores:

Actual scores

If the missing clinical component has weight > 4 in the overall score (see [Table 33](#)), then no imputation is performed. The SLEDAI-2K score will be missing.

If the missing clinical component has weight ≤ 4 in the overall score (see [Table 33](#)) or laboratory components missing, then the missing values will be imputed with the value of previous analysis visit. Only value assessed post-Day 1 dose (i.e. after baseline) can be used for imputation. If at least one item is still missing, then SLEDAI-2K score will be calculated based on available data.

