  lsmeans TreatmentGroup* SLEDAI_2K_screening / slicediff= SLEDAI_2K_screening
  oddsratio ilink cl;
  ods output Glimmix.LSMeans.SliceDiffs;
run;
```

Adjusted P-value:

The 12 raw p-values generated (for the two-primary endpoints and two key secondary endpoints with 3 treatment comparisons with placebo) are adjusted based on the hierarchical procedure by applying the methodology described in Section 14.1.2.4 (and further explained in Appendix 18.15). SAS PROC IML presented in Maurer 2014 will be used to generate the final adjusted p-values (i.e. adjusted for multiplicity).

MI process – MAR pattern: PROC MI with SAS

The following SAS code can be used to implement the MI with MAR pattern. The order of the SRI components must follow the one defined in the Section 14.1.2.4.

```
/******
STEP 1 : creation of monotone missing data structure
******/

/** _burn-in_NBITER_ will have to be adjusted by a convergence plot,
if convergence is not yet diagnosed after 200 iterations ***/
title "Step 1 : Create monotone structure" ;
proc MI data=<Dataset> out=outMAR1 seed=&seed. nimpute=&nimpute. noprint;
  var
  TreatmentGroup
  black (0=non-black 1=black)
  SLEDAI_2K_screening
  US (0=not US 1=US region)
  West (0=not Western Europe, 1=Western Europe region)
  Jap (0=not Japan region, 1=Japan region)
  SRIComp1_base SRIComp3_base
  SRIComp1_Day14 SRIComp2_Day14 SRIComp3_Day14

  /* continue to the last endpoint */

  ;
  mcmc chain=single initial=EM nbITER=200 NITER=100 impute=monotone ;
  EM MAXITER = 5000 ;
run ;

/******
```

```
STEP 2 : Apply multiple imputation
*****/
title "Step 2 : Apply MI procedure (MAR pattern)" ;
proc mi data=outMAR1 nimpute=1 seed=&seed. out=outMAR2 noprint;
  by _Imputation_;
  class TreatmentGroup race region SLEDAI_2K_screening;
  var
    TreatmentGroup race region SLEDAI_2K_screening
    SRIComp1change_Day14 SRIComp2_Day14 SRIComp3_Day14

  /* continue to the last endpoint */

;
  monotone regression;
run;
```

Then after applying the needed derivation of SRI score and the logistic analysis of interest for SRI-4, the next step consists in:

```
*****
STEP 4a : Pooling ODDS RATIOS and CI using Log Transformation
*****/
*** Log-transform odds ratio estimates and obtain standard error from confidence
intervals ***;
DATA lgsodds_t;
  SET lgsodds (WHERE=(INDEX(EFFECT,"TRT")));
  log_or_lr_value=LOG(ODDSRATIOEST);
  qn=quantile('NORMAL',.975);
  log_or_lr_se=(LOG(UPPERCL)-LOG(LOWERCL))/(2*qn);
RUN;
*** Combine transformed estimates;

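### Sensitivity Analysis #2 imputes the integer SLEDAI-2K change as an unrounded normal variable and cuts it at exactly 4 or 6 points, which modestly lowers imputed response rates (minor)

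*SAP*

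**What the plan says.** SAP Section 14.1.2.2, Sensitivity Analysis #2, imputes three SRI components and then rebuilds the response.

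- **SLEDAI-2K:** "SLEDAI-2K change from baseline total score will be imputed using SAS MI procedure". For the 4-point cut the text continues "point reduction will be re-derived from the imputed values", and for the 6-point cut "point reduction will be also re-derived from the imputed values". No rounding, range limit or midpoint rule is given.
- **PGA:** imputed as approximately normal and then brought back to the 0–3 scale. At the lower end, "Negative values will be imputed as 0".
- **BILAG criterion:** imputed as a 0/1 variable and then cut at the midpoint. "Values < 0.5 will be imputed as 0", and values above 0.5 become 1.

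The first step fills non-monotone gaps by MCMC, "assuming MAR and multivariate normality". The second step, in the sample code of Section 18.9.1, uses "monotone regression". That code has no rounding option, and the SRI components are not declared as class variables.

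Section 18.1.3 defines the SLEDAI-2K total as "calculated as the sum of the weights of the descriptors marked as present by the investigator". The weights in Table 33 are 8, 4, 2 and 1. Only fever, thrombocytopenia and leukopenia carry weight 1.

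**The concern.** Observed SLEDAI-2K changes lie on integers, mostly even ones, so both response cuts sit on values that subjects actually attain. A continuous normal imputation spreads that mass to either side of the cut. Draws between −3.5 and −4 are closest to an attainable −4, which is a response, but they are counted as failures. For a subject whose score can move only in even steps, the affected interval runs from −3 to −4. The same happens at −6.

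The plan maps the other two components back to their scales but not the one that separates SRI-4 from SRI-6. Imputed subjects therefore meet the SLEDAI criterion less often than observed subjects with the same underlying distribution. That is not what a missing-at-random analysis is meant to show. The pooled responder percentages by arm are a planned output, so the bias enters a reported table. This is also the only analysis of the primary endpoints that replaces non-responder imputation with a missing-at-random model, since Section 7 drops the completers analysis.

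**Working it through.** The plan gives no figure for this bias and no SD for SLEDAI-2K change, so there is nothing of its own to reproduce here. The SD below is an assumption.

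**Inputs**
- Cuts: 4 points (all subjects) and 6 points (HDA), Section 14.1.2.2.
- Score weights: Table 33.
- Planning response rates: SRI-4 40% against 60%; SRI-6 in HDA 30% against 55% (Section 8.2.1).
- Drop-out allowance: 5% (Section 8.2.1).
- SD of SLEDAI-2K change: assumed 3 to 6.

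**1. Analytic shortfall on the SLEDAI criterion.** Let p be the true rate on the score's own grid and h half the grid step (0.5 for integers, 1.0 for even numbers only). Cutting a normal variable at the exact threshold gives Φ(Φ⁻¹(p) − h/SD), so

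shortfall = p − Φ(Φ⁻¹(p) − h/SD).

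Example with p = 0.50 and SD = 4:
- Integer grid: 0.500 − Φ(−0.125) = 0.500 − 0.450 = 5.0 points.
- Even grid: 0.500 − Φ(−0.25) = 0.500 − 0.401 = 9.9 points.

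For p from 30% to 60%:

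| Assumed SD | Integer grid (points) | Even grid (points) |
|---|---|---|
| 3 | 5.5–6.6 | 10.4–13.2 |
| 4 | 4.2–5.0 | 8.1–9.9 |
| 5 | 3.4–4.0 | 6.6–8.0 |
| 6 | 2.8–3.3 | 5.5–6.6 |

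The overall range is about 3 to 13 points. The right-hand column needs a score that never moves by an odd number, which the weight-1 descriptors rule out as a general description.

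**2. Descriptor-level simulation.** Scores were built from descriptors with the SLEDAI-2K weights and assumed prevalences, 60,000 subjects per scenario. Week 52 was set missing at random in 20% and imputed by normal regression without rounding. Predictors were the HDA stratum, with or without the Week 48 change. The SD of change came out at 3.6 to 4.4.
- SRI-4 cut: 3.1 to 8.4 points too low.
- SRI-6 cut in HDA: 3.5 to 8.3 points too low.
- The shift was downward in every scenario.

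PGA, BILAG and treatment failure were not modelled. Full SRI response also requires those criteria, so its loss is somewhat smaller.

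**3. Effect on reported arm rates.** Assume 20% imputed, with the simulated shortfalls closest to the planning rates: 5.3 points (placebo) and 7.4 points (active).
- Placebo: 40 − 0.20 × 5.3 = 38.9%.
- Active: 60 − 0.20 × 7.4 = 58.5%.

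The falls are about 1.1 and 1.5 points. Across the whole simulated SRI-4 range they are 0.20 × 3.1 = 0.6 to 0.20 × 8.4 = 1.7 points. At the planned 5% the largest is 0.05 × 8.4 = 0.4 points.

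**4. Effect on the odds ratio.**
- True: (0.60/0.40) / (0.40/0.60) = 2.25.
- As imputed: (0.5852/0.4148) / (0.3894/0.6106) = 1.411/0.638 = 2.21.
- With 103 per arm, SE(log OR) = √(2 / (103 × 0.4 × 0.6)) = 0.28.
- The shift is ln 2.25 − ln 2.21 ≈ 0.017, or about 0.06 standard errors.

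**The case against.** The strongest reply is that this hardly matters.
- Sensitivity 2 is nominal and outside the multiplicity procedure. Its main result is an odds ratio, which barely moves.
- The bias has the same direction and similar size in all arms.
- The tipping-point analysis (Sensitivity 3) already runs through all combinations of responders among the missing, so it spans any shift of this size.
- A wholly missed visit takes the previous visit's SLEDAI-2K, PGA and BILAG values (Sections 18.1.1 to 18.1.3), which may leave fewer subjects to impute.
- That the values stay unrounded is inferred from the text's silence and from sample code. It is not stated outright.

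All of this stands as to importance, and it is why the point is minor. It does not remove the defect. Followed as written, text and code give a biased rate for one component while correcting the scale of the other two. The 5% allowance is also not a safe ceiling, because Section 7 enlarges the primary cohort for a potentially higher drop-out rate.

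A reader might also infer that the bias pulls this analysis onto the non-responder primary result, so that agreement is built in. The size does not support that. At an assumed mean of −4 and SD of 3.5, the integer-grid rate is Φ(0.5/3.5) = 55.7% and the as-written rate is 50.0%. The primary rule gives missing subjects 0%. The move is 5.7/55.7, about 10% of the distance (11.2/61.2, about 18%, on a purely even grid). The two analyses remain a real contrast.

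**Conclusion.** The defect is real and its direction is clear, but it is minor. The imputed rate of meeting the SLEDAI criterion is too low by about 3 to 8 points in the simulation, which rests on assumed prevalences. Analytically it is about 3 to 13 points, which rests on an assumed SD of 3 to 6. These figures concern imputed subjects and one criterion. A reader might take a double-figure understatement of SRI response as established, but that needs a purely even-step score and an SD towards the low end of the assumed range, and the documents support neither. Arm-level rates fall by about 1 to 1.5 points if 20% are imputed, and by under about 0.5 at 5%. A reader might also suspect that the trial's conclusion is at risk. It is not: the primary analysis does not use this imputation, and the odds ratio in the sensitivity analysis changes by a small fraction of its standard error.

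**What to change.** Impute SLEDAI-2K change in Step 2 by predictive mean matching (MONOTONE REGPMM), so that imputed values are observed scores. Changing Step 2 alone is not enough, because the Step 1 MCMC can fill a Week 52 SLEDAI-2K value when a later-ordered component is present, and that fill is continuous. Either map any such value to the nearest attainable score, or use FCS REGPMM for both steps. Then apply the 4-point and 6-point cuts. State the rule in Section 14.1.2.2 beside those for PGA and BILAG.

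Simpler repairs are weaker. In the simulation, rounding to the nearest integer left errors from +1.5 to about −4 points, mostly 0 to −3. Moving the cuts to 3 and 5 overcorrected by about 1 to 7 points.

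The programming cost is small: a changed imputation method, a mapping rule and a few sentences of text. Predictive mean matching depends on donor values at the edges of the score range. The primary analysis had been reviewed before version 4.0 (Sections 6.3 and 6.4), so a rerun must be labelled post hoc, as Section 4 requires. The report should also state which rule was actually applied.

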- Monotone missing data structure will be created as follows: intermediate (non-monotone) missing data will be multiply imputed using the Markov chain Monte Carlo (MCMC) method and assuming MAR and multivariate log normality. The SAS procedure PROC MI with the MCMC option will be used with seed number = 2005270018. The number of burn-in iterations will be set to 200, which is the default value. Nevertheless, if diagnosis plots show that the convergence has not yet occurred, this will be adjusted.
- Then the response (Severe BILAG A: Yes/No) will be imputed with treatment group, race, region, SLEDAI-2K total score (<10; >=10) and response at previous visit covariates.
- Imputation will be repeated 1000 times. Then depending of the visit of censored observation or of response, the time to first severe BILAG A flare will be computed as described for the non- sensitivity analysis. Estimate and associated standard error of Cox regression analysis applied on each imputed sample will be combined using MIANALYZE SAS procedure with the Rubin’s rules as described in Appendix 18.9.

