                    SLEDAI_2K_screening / RL TIES=DISCRETE;
  Hazardratio TreatmentGroup / DIFF=REF;
run;
```

In addition to the Cox regression model, the subgroup analysis can be implemented using the following code:

```
proc phreg data=<dataset>;
  class TreatmentGroup(ref='Placebo') SLEDAI_2K_screening;
  model AVAL*CNSR(1) = TreatmentGroup SLEDAI_2K_screening
                    TreatmentGroup*SLEDAI_2K_screening / TIES=DISCRETE;
  Hazardratio TreatmentGroup / DIFF=REF;
run;
```

For trend test for key secondary endpoint time to first severe (BILAG A) flare:

```
proc phreg data=<dataset>;
  class TreatmentGroup Region Race SLEDAI_2K_screening / param=GLM;
  model AVAL*CNSR(1) = TreatmentGroup Region Race
                    SLEDAI_2K_screening / TIES=DISCRETE;
  ESTIMATE "Trend linear in treatment" TreatmentGroup -3 -1 1 3;
  CONTRAST "Trend linear in treatment" TreatmentGroup -3 -1 1 3 / e;
run;
```

Sensitivity analysis of first severe BILAG A flare:

```
/******
  STEP 1 : creation of monotone missing data structure
******/

/** _burn-in_NBITER_ will have to be adjusted by a convergence plot,
if convergence is not yet diagnosed after 200 iterations ***/
title "Step 1 : Create monotone structure" ;
proc MI data=<Dataset> out=outMAR1 seed=&seed. nimpute=&nimpute. noprint;
  var
  TreatmentGroup
  black (0=non-black 1=black)
  SLEDAI_2K_screening
  US (0=not US 1=US region)
```

```
West (0=not Western Europe, 1=Western Europe region)
Jap (0=not Japan region, (1=Japan region)

Resp_base Resp_Day14-Resp_Day52;

/* continue to the last endpoint */

;
mcmc chain=single initial=EM nbITER=200 NITER=100 impute=monotone ;
EM MAXITER = 5000 ;
run ;

/*****
STEP 2 : Apply multiple imputation
*****/
title "Step 2 : Apply MI procedure (MAR pattern)" ;
proc mi data=outMAR1 nimpute=1 seed=&seed. out=outMAR2 noprint;
  by _Imputation_;
  class TreatmentGroup race region SLEDAI_2K_screening
    Resp_base Resp_Day14-Resp_Day52;
  var TreatmentGroup race region SLEDAI_2K_screening
    Resp_base Resp_Day14-Resp_Day52;
  monotone logistic;
run;

/*****
STEP 3 : Create dataset with Time to
*****/
This should be define in specification of ADAM and same rule should be applied to
outMAR2 dataset by imputation.

/*****
STEP 4 : Create estimate on imputed dataset
*****/
proc phreg data=<dataset>;
  by _Imputation_;
  class TreatmentGroup(ref='Placebo') Region Race SLEDAI_2K_screening;
  model AVAL*CNSR(1) = TreatmentGroup Region Race

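### The multiple-imputation sensitivity analysis imputes the binary BILAG criterion by linear regression cut at 0.5, which does not preserve its rate and tends to shrink the arm contrast among imputed values

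*SAP*

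**What the plan says.** SAP Section 14.1.2.2, Sensitivity Analysis #2, imputes the three SRI components and then rebuilds the response. The third component, no new BILAG A and at most one new BILAG B, "will be considered as a dichotomic response with value 1 when it is met and 0 otherwise". After imputation it is turned back into 0 or 1 by a cut: "Values < 0.5 will be imputed as 0" and "Values > 0.5 will be imputed as 1".

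The imputation has two steps. Intermittent gaps are "multiply imputed using the Markov chain Monte Carlo (MCMC) method and assuming MAR and multivariate normality". The remaining monotone gaps are filled by the Step 2 code in Appendix 18.9.1. There the classification statement is "class TreatmentGroup race region SLEDAI_2K_screening", which leaves the BILAG component continuous, and the method is "monotone regression".

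For the time-to-first-severe-flare sensitivity analysis, the monotone step in Appendix 18.9.2 lists the binary flare responses as classification variables and uses "monotone logistic". Its intermittent step is also a normal-type model, "assuming MAR and multivariate log normality" (Section 14.2.1). The SAP does not explain why the two binary BILAG variables are treated differently.

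**The concern.** Linear regression of a 0/1 variable can match its mean. Cutting the normal draws at 0.5 replaces that mean with the probability that a normal variable exceeds 0.5, which is generally a different number. The imputed component then has the wrong rate even when the missing-at-random assumption is true and the covariates are right.

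Sensitivity Analysis #2 is the missing-at-random counterpart to the non-responder rule used for both primary endpoints. Section 7 mentions a drop-out rate that may exceed expectation. A reader comparing this analysis with the primary one should see only the effect of the missing-data assumption, without an avoidable error from the imputation method.

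**Working it through.** The SAP states no figure for this analysis, so there is none to reproduce. It gives neither BILAG-component rates nor missing fractions at Week 52. Its only numerical anchor is the 5% drop-out in Section 8.2.1, and Section 7 expects possibly more without giving a number. The rates below are therefore assumed over a range.

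**1. Rate after rounding, no covariates.** A normal draw with mean p and variance p(1−p), cut at 0.5, gives 1 with probability Φ((p − 0.5)/√(p(1−p))).

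| True p | (p − 0.5)/√(p(1−p)) | Rate after cut | Error (points) |
|---|---|---|---|
| 0.70 | 0.20/0.458 = 0.436 | 0.669 | −3.1 |
| 0.80 | 0.30/0.400 = 0.750 | 0.773 | −2.7 |
| 0.90 | 0.40/0.300 = 1.333 | 0.909 | +0.9 |
| 0.95 | 0.45/0.218 = 2.065 | 0.981 | +3.1 |

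Between 0.5 and 1, the rate comes out too low up to about 0.88 and too high above that.

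**2. Arm contrast under the coded model.** Step 2 fits one regression per imputation with treatment as a covariate. The residual variance is therefore pooled over arms. With treatment as the only covariate, the imputed rate in an arm is Φ((p − 0.5)/s), where s² is the average of p(1−p) over the arms.

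- Two equal arms, 70% vs 95%: s² = (0.2100 + 0.0475)/2 = 0.12875, s = 0.359. The rates are Φ(0.557) = 71.1% and Φ(1.254) = 89.5%. The contrast falls from 25 to 18.4 points.
- Two equal arms, 80% vs 90%: s² = (0.16 + 0.09)/2 = 0.125, s = 0.354. The rates are Φ(0.849) = 80.2% and Φ(1.131) = 87.1%. The contrast falls from 10 to 6.9 points.
- Placebo 70% and three active arms at 95%: s² = (0.2100 + 3 × 0.0475)/4 = 0.0881, s = 0.297. The rates are 75.0% and 93.5%, a contrast of 18.5 points.

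**3. With covariates and missing-at-random drop-out.** A two-arm simulation (400,000 subjects per scenario) used treatment, previous SLEDAI change and previous BILAG status as covariates. It compared linear imputation plus rounding with logistic imputation. Three scenarios:

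| Missing (arm 0 / arm 1) | Arm | True rate among missing | Linear + cut | Logistic |
|---|---|---|---|---|
| 25.4% / 19.5% | 0 | 0.594 | 0.591 | 0.594 |
| | 1 | 0.687 | 0.661 | 0.687 |
| 21.1% / 16.5% | 0 | 0.906 | 0.966 | 0.908 |
| | 1 | 0.938 | 0.973 | 0.937 |
| 6.0% / 4.5% | 0 | 0.879 | 0.947 | 0.885 |
| | 1 | 0.925 | 0.962 | 0.924 |

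Over all scenarios the error among imputed subjects ran from about −3 to about +7 points. Logistic imputation was within about 0.7 points of the truth.

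**4. Dilution to the whole arm.** In the 21.1% / 16.5% scenario the error is 0.211 × 6.0 = 1.3 points in arm 0 and 0.165 × 3.5 = 0.6 points in arm 1. Averaged over arms the component rate moves from 0.943 to 0.952, about 1 point. The arm difference falls from 2.40 to 1.74 points, a loss of about 0.7. With 4–8% missing the average moves by about 0.3 points or less.

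**5. Effect on SRI.** In a separate missing-at-random simulation with about 9% missing, SRI-4 moved by less than 0.1 point.

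**The case against.** The strongest reply is that nothing turns on this. Sensitivity Analysis #2 reports nominal p-values and sits outside the testing hierarchy of Section 14.1.2.4. The tipping-point analysis also tests robustness to missing responses and does not use this imputation. The BILAG criterion is one of three imputed components. The carry-forward rules for missed visits in Appendices 18.1.1 to 18.1.3 may reduce what reaches the imputation. Version 4.0 of the SAP follows review of the primary results, so a rerun now would be post hoc. All of this stands, and it limits the size and urgency of the point. It does not make the rounding rule correct.

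The flare analysis is also an imperfect model to copy. Only its monotone step is logistic, and no rounding is stated before the values from its normal-type first step enter the classification statement. That stands too. The comparison shows that the SAP already uses logistic imputation elsewhere, not that its flare imputation is fully specified.

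A reader might infer from the table in step 1 of the working that rounding exaggerates treatment differences: applied to each arm separately, 70% vs 95% becomes 66.9% vs 98.1%, about 31 points instead of 25. The documents do not support this. That calculation gives each arm its own variance, whereas the Appendix 18.9.1 code fits a single regression with treatment as a covariate. Under that model the contrast shrinks, as the calculations and the simulation both show. Even the arm-by-arm formula does not stretch differences in general: 50% vs 70% shrinks from 20 to 16.9 points.

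**Conclusion.** The point holds as a minor analysis-choice defect. The stated method does not preserve the rate of the binary BILAG component, and under the coded model it tends to attenuate the arm contrast among imputed values.

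The simulated whole-trial effect is small at the assumed missing fractions, and the effect on SRI-4 and SRI-6 should be smaller still. These sizes depend on assumed component rates, missing fractions and covariate strength, none of which the SAP gives. Only Sensitivity Analysis #2 is affected. The primary non-responder analysis of the two primary endpoints does not use this imputation, so nothing here casts doubt on it.

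**What to change.** In Section 14.1.2.2 and Appendix 18.9.1:

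- After Step 1, round component 3 to 0/1, only for the intermittent values that the normal-model MCMC has filled in, so that the classification statement receives only 0/1 values.
- In Step 2, add the component-3 visit variables to the CLASS statement and impute them with monotone logistic regression. Keep monotone linear regression for SLEDAI-2K change and PGA.
- Delete the 0.5 cut for values imputed in Step 2.

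Rounding in Step 1 leaves some distortion for intermittent gaps. Fully conditional specification with a logistic model for component 3 throughout is an alternative that avoids it.

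The cost is a few lines of code and checks for separation where BILAG failures are sparse within a visit or stratum. Because the primary results were reviewed before this SAP version, a rerun should be identified in the CSR as post hoc, in line with Section 4.
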